#### **5.4.6 Exclusion Criteria**

Patients will be excluded from participation in the study if any of the following conditions exist:

1. History of HCT;
2. Pregnancy or breastfeeding;
3. Known or suspected allergy to interferon gamma-1b or related products;
4. Participation in simultaneous therapeutic study that involves an investigational study drug or agent within 4 weeks of study enrollment;
5. ALT greater than 3 fold higher than normal;
6. Thalassemia or other hemoglobinopathy due to potential for inhibition of erythropoiesis and/or increased red blood cell destruction (18–21); or
7. Left ventricular ejection fraction measured by ECHO of <30%; or
8. Any other social or medical condition that the Investigator believes would pose a significant hazard to the subject if the investigational therapy were initiated or be detrimental to the study.

#### **5.4.7 Participation of Females**

The fetal risks associated with IFN- $\gamma$ 1b are not known, but pre-clinical animal data demonstrate some risk (Pregnancy category C). Females of childbearing potential must agree not to become pregnant during the study and must have a pregnancy test at each study visit (baseline, month 3, month 6, and month 12). Because of the risk involved, sexually active subjects and their partners must use two methods of birth control. They must continue to use both methods until 1 month after stopping study drug. Two of the birth control methods listed below may be chosen:

- Hormonal contraception

- Male or female condoms with or without a spermicidal
- Diaphragm or cervical cap with a spermicidal
- Intrauterine device (IUD)

#### **5.4.8 Study subject Exit/Discontinuation Criteria**

National Cancer Institute (NCI) Common Terminology Criteria for Adverse Events (CTCAE), Version 4 will be used to define an Adverse Event (AE). The CTCAE Grades 1 through 5 with unique clinical descriptions of severity for each AE will be used and defined as follows:

Grade 1 Mild; asymptomatic or mild symptoms; clinical or diagnostic observations only; intervention not indicated.

Grade 2 Moderate; minimal, local or noninvasive intervention indicated; limiting age-appropriate instrumental Activities of Daily Living (ADL)\*.

Grade 3 Severe or medically significant but not immediately life-threatening; hospitalization or prolongation of hospitalization indicated; disabling; limiting self care ADL\*\*.

Grade 4 Life-threatening consequences; urgent intervention indicated.

Grade 5 Death related to AE.

A Semi-colon indicates 'or' within the description of the grade.

\*Instrumental ADL refer to preparing meals, shopping for groceries or clothes, using the telephone, managing money, etc.

\*\*Self care ADL refer to bathing, dressing and undressing, feeding self, using the toilet, taking medications, and not bedridden.

Subjects will discontinue participation in study for any unexplained CTCAE Grade 3 or higher that is not reasonably related to the underlying disease process or treatments. In addition, subjects will discontinue study participation if any of the following conditions exist:

1. Subject voluntarily withdraws from the study.
2. Subject's death.
3. Subject completes the protocol.
4. Pregnancy.

5. Subject acquires any of the listed exclusion criteria.
6. Subject is non-compliant with the protocol. For example, missing the Month 3 visit (no visit by 120 days after beginning therapy).
7. Subject's well-being, in the opinion of the Investigator would be compromised by continuation in the study.
8. Subject contracts an intercurrent illness that requires treatment not consistent with the protocol requirements.

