#### **6.4 Unscheduled Study Visits**

Additional visits will be scheduled with study physicians or local physicians as needed throughout the study period to address concerning signs or symptoms reported by subjects.

Subjects may withdraw voluntarily from the study at any time. If a subject opts to discontinue, attempts will be made to schedule and conduct an Early Termination visit for medical assessment.

If a subject withdraws after an AE, they will be followed until resolution of the issue or until their condition is stable. In the event that a subject becomes pregnant, then discontinuation, reporting, and follow-up procedures outlined in Section 8.3.4 will be followed.

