#### **6.8 Subject Withdrawal**

Subjects will be encouraged to complete the study; however, they may voluntarily withdraw at any time. If a subject is withdrawn prior to study completion, attempts will be made to schedule and conduct an Early Termination visit for medical assessment. If a subject cannot be contacted after 5 telephone calls and 3 letters, they will be considered lost to follow-up.

Subjects who discontinue study medication (e.g., due to non-compliance, side effects, etc.) will be asked to remain in the study for follow-up per the study schedule to preserve the ability to perform a

safety analysis. If a subject or their legal guardian (as applicable) withdraws consent to participate in the study, attempts will be made to obtain permission to record survival and adverse event (malignancy, hospitalization for infection) data at the 12-month study point.

As long as the link between the sample ID code and the subject name is maintained by the clinical study site, it will be possible for subjects to ask that their samples be withdrawn. However, we anticipate this link will be destroyed at some point in the future, after which withdrawal of samples will not be possible. In addition, once DNA samples have been provided to collaborators, we cannot guarantee that all samples will be able to be tracked down.

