# **7 Data Collection and Analysis**

## **7.1 Subject Population(s) for Analysis**

- Treatment-compliant population: Any subject who received at least 85% of prescribed doses and attended all scheduled study visits.
- Safety population: All subjects who receive any amount of treatment.

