## **8.4 Safety Monitoring Plan**

The plan for ensuring subject safety will include the following elements:

1. Clinical procedures will only be performed by properly trained personnel who are qualified by training and licensure to perform the procedures.
2. Investigator and all study personnel have completed required training regarding Human Subject Protections. All personnel will comply with all related regulations and laws.

3. Patients will be rigorously screened against inclusion/exclusion criteria to ensure that their participation is safe.
4. Adverse events and SAEs will be assessed and followed throughout study. Subjects will have contact information to enable them to contact study personnel easily and quickly.
5. Study data and information will be kept confidential and managed in accordance with requirements of Health Insurance Portability and Accountability Act of 1996 (HIPAA). All data will be stored in locked offices and not released without subject permission.
6. Subject may discontinue participation at any time, for any reason. Any subject who fails to complete the research procedures within acceptable parameters, or is unable to safely tolerate participation in the study will be withdrawn.
7. Institutional Review Board approval will be obtained.
8. Monitoring will be conducted by an external Data and Safety Monitor as described in the Data and Safety Monitoring Plan (appendix A).

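### Section 5.4.8 item 5, read literally, ends study participation for a drug-related ALT rise above 3-fold normal, which works against the off-drug follow-up in 6.8 and overlaps with dose reduction in 6.3.6

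*Combined protocol and SAP*

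**What the plan says.** Four parts of the combined protocol and SAP bear on a treated subject whose ALT rises.

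- **Study exit (5.4.8).** The numbered list opens with "subjects will discontinue study participation if any of the following conditions exist". Item 5 reads "Subject acquires any of the listed exclusion criteria". One of the criteria in 5.4.6 is "ALT greater than 3 fold higher than normal". The sentence just before the list sends subjects off study "for any unexplained CTCAE Grade 3 or higher that is not reasonably related to the underlying disease process or treatments".
- **Follow-up off drug (6.8, second paragraph).** "Subjects who discontinue study medication (e.g., due to non-compliance, side effects, etc.) will be asked to remain in the study for follow-up" on the study schedule. The stated reason is to keep the safety analysis possible.
- **Dose reduction (6.3.6).** The dose may be lowered case by case for drug-related events, and raised liver function tests are one of the examples.
- **Safety monitoring (8.4 item 6).** A subject who "is unable to safely tolerate participation in the study will be withdrawn".

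Liver function tests are scheduled on treatment at weeks 4 and 6 and months 3, 6, 9 and 12 (Table 1 with footnote c; 6.3.2).

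**The concern.** The protocol does not separate stopping the drug from leaving the study. The Grade 3 sentence in 5.4.8 exempts events related to treatment, but the numbered list has no such exemption. As written, a drug-related Grade 3 event does not by itself force an exit, while a drug-related ALT above 3-fold does. The same ALT result could lead to dose reduction (6.3.6), a drug stop with continued visits (6.8) or study exit (5.4.8), and two sites could reasonably choose differently.

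What is at stake is scheduled safety information after the drug is stopped. Under the exit rule it is lost selectively, in subjects who did not tolerate the drug, in a 10-subject study whose primary objective includes tolerability. That is the information 6.8 sets out to keep.

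**Working it through.** The plan states no figure on this point, so there is none to reproduce. The check sets the texts side by side and counts what one exit costs.

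**1. Does item 5 reach ALT?** Yes, by cross-reference to 5.4.6 item 5. The words about treatments qualify only the Grade 3 sentence. The list is introduced as an addition to that sentence and carries no qualifier.

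**2. Can the trigger occur on schedule?** Yes. Among the criteria that concern drug safety (ALT, ejection fraction, allergy), only ALT has a scheduled repeat test. The echocardiogram is done at screening only (Table 1).

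**3. Scheduled liver-test draws forgone.** There are six post-baseline draws. After a trigger at draw k, 6 − k remain.

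| Trigger | k | Later draws forgone | Month 12 visit lost |
|---|---|---|---|
| Week 4 | 1 | 5 | yes |
| Week 6 | 2 | 4 | yes |
| Month 3 | 3 | 3 | yes |
| Month 6 | 4 | 2 | yes |
| Month 9 | 5 | 1 | yes |

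One affected subject is 1/10 = 10% of the planned sample.

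**4. Would the paired tests lose subjects?** Planned injections are 3 × 52 = 156. Taking months 3, 6 and 9 as weeks 13, 26 and 39, the numbers given by the five trigger times are 12, 18, 39, 78 and 117, that is 8%, 12%, 25%, 50% and 75%. The treatment-compliant population in 7.1 is "Any subject who received at least 85% of prescribed doses and attended all scheduled study visits". Measured against the 12-month course, 85% of 156 is 132.6, so 133 injections, reached in week 45 (133/3 = 44.3). A subject who stopped drug at any of these triggers would be outside that set whether or not visits continued. Section 7.2.2 names no analysis set for the paired tests, so no loss of precision can be attributed to the exit rule.

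**5. Cost of keeping a subject in follow-up.** Section 6.9 pays up to $1,500 travel plus $50 per visit, so $1,550. Reimbursed visits remaining (months 3, 6, 12):
- after week 4 or 6: 3 × $1,550 = $4,650
- after month 3: 2 × $1,550 = $3,100
- after month 6 or 9: 1 × $1,550 = $1,550

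Month 9 is a laboratory draw with no travel payment in 6.9.

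**The case against.** The strongest reply is that the texts can be reconciled. The first paragraph of 6.8 covers subjects withdrawn from the study, and the second covers subjects who stop medication. On that view a 5.4.8 exit falls under the first paragraph and there is no contradiction. The second paragraph is also a request to the subject, not a requirement. This stands: a reader might infer that the two sections cannot both be followed, and the documents do not go that far. The reconciliation does not remove the loss, however. It puts the drug-related ALT rise among the exits, and the scheduled visits are still forgone.

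Several provisions soften that loss:
- For a subject who withdraws after an adverse event, 6.4 says "they will be followed until resolution of the issue or until their condition is stable". Section 8.2 similarly follows events to resolution, stabilisation or exclusion of a study cause, and has possibly related later serious events reported.
- An Early Termination visit is attempted (6.8), though neither Table 1 nor Appendix B lists its content.
- Anti-drug antibody samples continue after the last dose (Table 1 footnote g; Appendix B places these under antibody-positive subjects).
- Section 6.6 lets the sponsor and investigator agree to keep an individual subject in the study after a deviation.

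These cover the event or the individual case. They do not restore the schedule, and none ranks 5.4.8 against 6.8.

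A reader might also infer a second conflict over non-compliance, which is an exit in 5.4.8 item 6 and a reason to stay in 6.8. That depends on applying item 6 to missed doses. Its only example is a missed Month 3 visit, which 6.3.1 also treats as withdrawal, so the documents do not establish this conflict.

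**Conclusion.** The point holds as a minor one. Read literally, item 5 ends participation for a drug-related ALT above 3-fold normal. This works against the stated purpose of 6.8 and leaves the boundary with 6.3.6 undefined. The size is 1 to 5 scheduled liver-test draws and the month 12 visit per affected subject, partly offset by event follow-up.

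A reader might infer harm to the primary result or to power. The documents do not support either. The subject has stopped drug under either rule, so the continued-treatment count is the same, and anyone who received any treatment stays in the safety population (7.1). The documents give no rate of ALT rise, so no study-level loss can be stated.

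The conclusion assumes that item 5 is applied as written and that 6.6 is not used routinely to keep such subjects.

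**What to change.** 1. **5.4.8 item 5.** Add: *If a safety-type exclusion criterion is met on study (ALT above 3-fold normal, LVEF below 30%, allergy to the drug, or an investigator-judged hazard of the drug under exclusion 8), study drug is stopped and the subject is asked to remain in scheduled follow-up to month 12 under 6.8.* Keep pregnancy, HCT and entry into another investigational-drug study as exits.
2. **6.3.6.** State that dose reduction for raised liver tests applies up to the 3-fold ALT threshold, above which item 5 applies.
3. **8.4 item 6.** Keep withdrawal for subjects who cannot safely continue study procedures. Add that subjects who cannot tolerate the drug stop it and are followed under 6.8.
4. **7.2.2.** Report data after drug discontinuation separately in the safety analysis.

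Item 6 of 5.4.8 needs no change. If it is touched, limit the edit to a clarification that missed doses alone lead to follow-up under 6.8, while a missed Month 3 visit remains an exit.

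The cost is an amendment to wording, plus a few already planned visits for off-drug subjects: at most $4,650 per subject in travel and stipend, and the scheduled tests, whose cost the documents do not give. The existing ALT threshold is kept. The gain is mainly scheduled safety follow-up; the month 12 efficacy comparison gains little.

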## **6 Study Procedures**

### **6.1 Informed Consent and Assent**

Each subject or the subject's parent/legal guardian will be provided a consent form describing this study and providing sufficient information to make an informed decision about their participation in this study. The consent form will be submitted with the protocol for review and approval by the IRB for the study. The formal consent of an adult subject or minor subject's parent/legal guardian, using the IRB-approved consent form, must be obtained before that subject is submitted to any study procedure. This consent form must be signed by the subject and/or parent/legal guardian, and the Investigator-designated research professional obtaining the consent. A blank copy of the IRB-approved form must be kept on-site by the Investigator.

Consent process (in person) will take place in a private room. We will ensure that there is an ample waiting period available between informing the prospective subject and obtaining the consent. There will be dialogue during each contact with the subject to ensure ongoing consent is voluntary.

#### **Non-English Speaking Subjects**

- Spanish speaking subjects will be included.
- Telephone or interpreter will be used.

#### **Subjects who are not yet adults (infants, children, teenagers)**

- Subjects in the United States are considered minors if they are 17 years or younger, with the exception of Alabama (18 years), Nebraska (18 years or upon marriage), and Mississippi (20 years)
- Parental permission will be obtained from:
  - One parent even if the other parent is alive, known, competent, reasonably available, and shares legal responsibility for the care and custody of the child.

- Parental or guardian (as defined by DHHS and FDA regulations) consent will be obtained. A guardian must provide written documentation of the legal ability to consent to for the child's participation in research. A copy of this documentation will be kept with the consent document.
- Assent will be obtained from all minor subjects aged 7 to 17 years.
- Assent will be documented with their signature on the assent form.

### **Adults Unable to Consent**

The individuals from whom permission will be obtained are the following in descending order of priority:

- The person's agent pursuant to an advance health care directive.
- The conservator or guardian of the person having the authority to make health care decisions for the person
- The spouse of the person
- An individual as defined in Section 297 of the Family Code
- An adult son or daughter of the person
- A custodial parent of the person
- Any adult brother or sister of the person
- Any adult grandchild of the person
- An available adult relative with the closest degree of kinship to the person

### **The process for assent of the subjects is as follows:**

- Assent will be required of all subjects age 7-17 years [except for Alabama (age 7-18 years), Nebraska (age 7-18 years or upon marriage), and Mississippi (age 7-20 years)] and for cognitively impaired adults.
- The process for assent will include reviewing the assent document with the subject and their parent/guardian in a verbal face-to-face discussion, asking them for questions and discussing these, then asking the subject to sign and date the assent document if they would like to participate in the study.
- Assent will be documented in a progress note.

## **6.2 Laboratory Testing Procedures**

### **6.2.1 Specimen Preparation**

Specimens for analysis will be collected as described in Table 2 at the time points indicated in Table 1. Venipuncture will be performed by trained certified nursing assistants, nurses, nurse practitioners, or physicians and collection and handling will be per the manufacturer's recommendations. A central venous catheter may be utilized for all blood sampling if the patient currently has one. Serum, plasma, and urine will be collected and stored at -80°F.

**Table 2. Laboratory Analytes and Collection Information.**

Analyte	Specimen	Tube Type	Notes	Batched at end of study?	Volume
High sensitivity erythrocyte sedimentation rate ( ESR )	Plasma	K 2 EDTA (purple-top tube)	Quest/Fairview	no	8 mL blood (2 tubes)
Bone specific alkaline phosphatase ( BAP )	Plasma	K 2 EDTA (purple-top tube)	[name] lab (store [name] lab)	yes	
Type 1 procollagen ( P1NP )	Plasma	K 2 EDTA (purple-top tube)	[name] lab (store [name] lab)	yes	
Osteoprotegerin ( OPG )	Plasma	K 2 EDTA (purple-top tube)	[name] lab (store [name] lab)	yes	
C-telopeptide ( CTX )	Plasma	K 2 EDTA (purple-top tube)	[name] lab (store [name] lab)	yes	
Tartrate resistant acid phosphatase type 5b ( TRAP5b )	Plasma	K 2 EDTA (purple-top tube)	[name] lab (store [name] lab)	yes	
Receptor activator of nuclear factor- $\kappa$ B ligand ( RANKL )	Plasma	K 2 EDTA (purple-top tube)	[name] lab (store [name] lab)	yes	
Complete blood count with differential ( CBCD )	Whole blood	K 2 EDTA (purple-top tube)	Quest/Fairview	no	
Immunologic phenotyping (CD3, 4, 8, 14, 15, 16, 19, 34, 56)	Whole blood	K 2 EDTA (purple-top tube)	Fairview	no	4 mL (1 tube)
Genetic testing for Carbonic Anhydrase II ( CAII ), Chloride Channel 7 ( CLCLN7 ), Osteopetrosis-associated Transmembrane Protein 1 ( OSTM1 ), RANKL, T-cell Immune Regulator 1 ( TCIRG1 ) gene mutations	Whole blood	K 2 EDTA (purple-top tube)	Fairview	no	4 mL (1 tube)
Liver function tests ( LFT )	Serum	SST (red-top tube)	Quest/Fairview	no	10 ml blood (2 tubes)
25-hydroxy vitamin D ( 25OHD )	Serum	SST (red-top tube)	Quest/Fairview	no	
Calcium	Serum	SST (red-top tube)	Quest/Fairview	no	
Intact parathyroid hormone ( iPTH )	Serum	SST (red-top tube)	Quest/Fairview	no	
Basic metabolic panel ( BMP )	Serum	SST (red-top tube)	Quest/Fairview	no	
Creatinine kinase - BB isoenzyme ( CK-BB )	Serum	SST (red-top tube)	[name] lab (store [name] lab)	yes	
Anti-drug antibodies ( ADA )	Serum	SST (red-top tube)	Intertek (store [name]/[name] labs)	yes- at month 12 visit	4 ml blood
Storage	Serum	SST (red-top tube)	[name]/[name] labs	NA	5 ml blood
Storage	Plasma	K 2 EDTA (purple-top tube)	[name]/[name] labs	NA	4 ml blood
Storage	Urine	sterile container	[name]/[name] labs	NA	8 ml urine
Urine pregnancy test, calcium to creatinine ratio ( ca:cr ) and urinalysis ( UA )	Urine	sterile container	Quest/Fairview POC UPT	no	10 ml urine
Ex vivo assays ([name] Lab)	Whole Blood	K 2 EDTA (purple-top tube)	[name] lab	no	10 ml (1 tube)
RNA expression	Whole Blood	PAXgene RNA tube	[name] lab	yes	2.5 ml
DNA	Buffy coat	K 2 EDTA (purple-top tube)	[name] lab	NA	10 ml

## 6.2.2 Research Specimen Handling and Storage (See Manual of Operations for instructions for non-LA BioMed sites)

### Samples for Bone Biomarkers and Storage

Plasma. Collect blood in 3 purple-top (ethylenediaminetetraacetic acid [EDTA]) tubes (4 mL each). After collection, thoroughly mix the tube by gentle inversion 8 times. Label the tube with the Subject's Study ID number, study visit, date of visit, and "plasma". **Do not write the subject's name or any other identifying information on the blood tube.** Place the tube upright in a rack in the refrigerator (2 to 8°C) until processed and stored at -80°C.

If need to transport to the lab for processing, wrap the tube in a paper towel and place it in a plastic bag with an absorbent pad. Place the plastic bag containing the tube in a Styrofoam mailer with a frozen gel pack or on ice. The gel pack will ensure refrigerator temperature (2 to 8°C) during transport to the laboratory.

2 tubes: Centrifuge for 15 minutes at 4000 x g within 30 minutes of collection. Aliquot 0.5 ml into each 2 ml cryovial (8 cryovials) and store samples at -80°C.

1 tube: Invert 8-10 times immediately after drawing. Keep tube cooled on ice, or with a cold pack, or in a 4C refrigerator. Transport to Translational Genomics & Population Sciences laboratory on ice for processing and storage of buffy coat.

Serum. Collect blood in 2 red-top (serum separator tube [SST]) tubes (5 mL each). After collection, allow blood to clot for 30 minutes. Label the tube with the Subject's Study ID number, study visit, date of visit, and "serum". **Do not write the subject's name or any other identifying information on the blood tube.** Place the tube upright in a rack in the refrigerator (2 to 8°C) until processed and stored at -80°C.

If need to transport to the lab for processing, wrap the tube in a paper towel and place it in a plastic bag with an absorbent pad. Place the plastic bag containing the tube in a Styrofoam mailer with a frozen gel pack or on ice. The gel pack will ensure refrigerator temperature (2 to 8°C) during transport to the laboratory.

Centrifuge for 15 minutes at 4000 x g within 30 minutes of collection. Aliquot 0.5 ml into each 2 ml cryovial (10 cryovials) and store samples at -80°C.

